10.8. Figures to Present

- Graph displaying recruitment rate over time (CHRONOS-A and CHRONOS-B), for patients recruited to the trial before¹ the Covid-19 pandemic
- Graph displaying recruitment rate over time (CHRONOS-A and CHRONOS-B), for patients recruited to the trial during/after² the Covid-19 pandemic
- Graph displaying actual vs target recruitment rate over time (CHRONOS-A and CHRONOS-B), for patients recruited to the trial before¹ the Covid-19 pandemic
- Graph displaying actual vs target recruitment rate over time (CHRONOS-A and CHRONOS-B), for patients recruited to the trial during/after² the Covid-19 pandemic
- Graph displaying randomisation rate over time (CHRONOS-A and CHRONOS-B), for patients recruited to the trial before¹ the Covid-19 pandemic
- Graph displaying randomisation rate over time (CHRONOS-A and CHRONOS-B), for patients recruited to the trial during/after² the Covid-19 pandemic.

¹Patients were recruited before the Covid-19 pandemic if they were recruited to the trial before 05/03/2020 (see Section 10.1)

²Patients were recruited during/after the Covid-19 pandemic if they were recruited to the trial after 05/03/2020 (see Section 10.1).

CHRONOS

11. Statistical Requirement for Early Termination of the Study

For a predicted sample size of 60 participants per trial (CHRONOS-A and CHRONOS-B), the 95% confidence interval for an estimated recruitment rate of 33% is (0.211, 0.449). Progression to the main stage will be initiated if the recruitment rate is above 21.1%.

If the recruitment rate is below 21.1%, the results of the feasibility analysis suggest that the trial is unfeasible and should be stopped. The result will be presented to the TSC, who will make the final decision, based on the evidence shown, as to whether the trial will continue to main stage. If the recruitment rate is between 21.1% and 33%, then remedial work will be implemented to improve the recruitment rate in the main stage of the trial. If the recruitment rate is greater than or equal to 33%, the trial will be deemed feasible.

If the trial does not proceed to the main stage following the analysis of the pilot, patients will be followed up for a minimum of 3 months and will then revert to standard of care in which the clinical care provided to patients will not differ from the clinical follow-up stipulated in this protocol. At the end of the study patients will continue to be followed up locally within their recruitment centres with the ICE (European Registry for Cryosurgical Ablation of the prostate, EuCAP) or the HEAT international HIFU registry as per NICE guidelines IPG432/IPG42.

12. Imperial Prostate Trial Steering Committee

A combined TSC and DMEC is in place to provide overall supervision of the trial and ensure that it is being conducted in accordance with the principles of Good Clinical Practice (GCP) and the relevant regulations. The TSC should agree the trial protocol and any protocol amendments and provide advice to the investigators and the Trial Management Group (TMG), via Imperial Clinical Trials Unit (ICTU) on all aspects of the trial.

The TSC should meet at least annually, although there may be periods when more frequent meetings are necessary.

13. Amendments to Version 1.0

CHRONOS

14. References

- 1. Cancer Research UK. Prostate cancer statistics 2014. Available from: http://www.cancerresearchuk.org/health-professional/cancer-statistics/statistics-bycancertype/prostate-cancer.

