5.1. Primary Outcome Measures

Feasibility of recruitment, acceptance of randomisation and compliance to allocated arm.

- Recruitment is defined as total number of patients recruited (consented) out of the total number of patients approached.
- Randomisation is defined as the total number of patients randomised out of the total number of patients recruited (consented).
- Compliance comprises of treatment compliance (CHRONOS-A and CHRONOS-B) and drug compliance (CHRONOS-B):
 - o Treatment compliance (CHRONOS-A and CHRONOS-B):
 - Proportion of patients who underwent treatment (Focal therapy ((CHRONOS-A and CHRONOS-B)), Radiotherapy/Brachytherapy or Prostatectomy (CHRONOS-A)) as recorded by date of treatment and completed treatment details recorded at Visit 2/3 (treatment visit)
 - o Drug compliance (CHRONOS-B). This will be measured in two ways:
 - Proportion of patients who returned their empty blister pack (yes/no), as recorded at Visit 3.
 - Proportion of patients who were given the drug (recorded at Visit 2) and who did not have a registered protocol deviation (stating that the drug was taken for less than 8 weeks).

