6.6.1. CHRONOS-A

A two-arm RCT will recruit 1190 patients over a total recruitment and follow-up period of 8 years. The number and nature of centres involved would require between 1-2 patients recruited per-centre per-month. At a conservative rate, we expect to recruit 60 patients in the Pilot Stage in 6 centres over 12-months.

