9.3. Primary End Point Analysis

The proportions of patients who opted for CHRONOS-A and CHRONOS-B will be reported.

The primary analysis of the internal pilot will calculate the mean number of patients recruited and randomised per month, per centre (including only the months in which the centre is open and recruiting). Overall recruitment and randomisation rates will also be calculated, along with their corresponding 95% confidence intervals. Recruitment rate is calculated as the number of participants recruited out of the total number approached. Randomisation rate is calculated as the number of participants randomised out of the total number recruited. Graphs displaying the recruitment and randomisation rates over time will be presented. A graph displaying the actual vs target recruitment rates will also be presented. These analyses will be conducted for CHRONOS-A and CHRONOS-B.

Compliance will be summarised using the CONSORT diagram for the internal pilot (see Section 1.1.1) which includes, the number of men who have withdrawn or been lost to follow-up (with reasons), and the number who completed each stage within each treatment arm. There will be a separate CONSORT for CHRONOS-A and CHRONOS-B.

Summary statistics for time between consent and randomisation, and randomisation and treatment will be presented by treatment arm. Summary statistics will also be presented for time between consecutive visits, by treatment arm.

For CHRONOS-B only, summary statistics will also be presented for time between randomisation and start of neoadjuvant treatment, and time between start of neoadjuvant treatment and start of focal therapy.

Treatment, for CHRONOS-A and CHRONOS-B, is recorded at Visit 2 (Treatment Visit). For focal therapy arms (CHRONOS-A (Focal arm) and CHRONOS-B) treatment is recorded by date of treatment and completed treatment details at Visit 2. For the radical arm of CHRONOS-A, treatment is recorded by date of visit 2 and completed treatment details on Radiotherapy/Brachytherapy Log and Prostatectomy Log at Visit 2. The proportions of patients in each treatment arm who underwent treatment will be presented, along with their corresponding 95% confidence intervals.

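### The 21.1% feasibility cut in SAP section 11 is a confidence limit computed on 60, the expected number recruited, although the recruitment rate is defined on the number approached

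*SAP*

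**What the plan says.** SAP section 11 sets the rule for moving from pilot to main stage. It starts from a planned size: "For a predicted sample size of 60 participants per trial (CHRONOS-A and CHRONOS-B"). It then says that "the 95% confidence interval for an estimated recruitment rate of 33% is (0.211, 0.449"), and builds three bands on that interval:

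- **33% or more:** the trial is deemed feasible.
- **21.1% to 33%:** "If the recruitment rate is between 21.1% and 33%, then remedial work will be implemented".
- **Below 21.1%:** "If the recruitment rate is below 21.1%, the results of the feasibility analysis suggest that the trial is unfeasible and should be stopped". For this band the SAP adds: "The result will be presented to the TSC, who will make the final decision, based on the evidence shown".

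The rate being judged is defined elsewhere in the SAP. Section 5.1: "Recruitment is defined as total number of patients recruited (consented) out of the total number of patients approached". Section 9.3: "Recruitment rate is calculated as the number of participants recruited out of the total number approached". Section 10.4 repeats this definition, and the footnote to Table 2.3 also names people approached as the denominator.

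The 60 comes from the sample size sections. For CHRONOS-A (6.6.1), "we expect to recruit 60 patients in the Pilot Stage in 6 centres over 12-months", and section 6.6.2 says the same for CHRONOS-B. Protocol sections 8.1.1 and 8.2 agree, and the treatment group tables divide the same 60 into arms (30+30 and 20+20+20). Neither document states how many men are expected to be approached.

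**The concern.** A confidence interval for a proportion needs the denominator of that proportion. Section 11 appears to use 60, which is the expected numerator (men recruited), where the number approached belongs. The two readings of 60 cannot both hold: if only 60 men were approached, a 33% rate would yield about 20 recruits, not 60.

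The lower limit is the only number separating a trial sent for remedial work from one put to the steering committee with a recommendation to stop. If it rests on the wrong denominator, it is wider of the target than the stated construction allows, and a pilot recruiting well short of 33% can escape the stop recommendation. The SAP offers no other reason for choosing 21.1%.

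**Working it through.** **Inputs.** Target rate p = 0.33, 95% level and n = 60 (SAP section 11); rate = recruited/approached (SAP 5.1, 9.3, 10.4, Table 2.3 footnote); 60 expected recruits per trial (SAP 6.6.1 and 6.6.2).

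**1. Reproduce the printed interval.** The simple normal-approximation (Wald) interval is p ± 1.96 × √(p(1 − p)/n).

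- Standard error: √(0.33 × 0.67/60) = 0.0607.
- Half-width: 1.96 × 0.0607 = 0.119.
- Interval: 0.33 ± 0.119 = (0.211, 0.449), as printed.

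Solving for n from a half-width of 0.119 gives 0.33 × 0.67 × (1.96/0.119)² = 59.98. Wilson, Clopper-Pearson, Agresti-Coull, Jeffreys and continuity-corrected intervals at n = 60 do not match. The denominator used was therefore 60.

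**2. Number approached implied by 60 recruits.** 60/0.33 = 181.8, or about 182. Conversely, 60 approached gives 0.33 × 60 = 19.8 recruits.

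**3. Same formula on the number approached.** The range is an assumption, because the documents give no figure.

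| Approached | 95% interval for 33% | Lower limit minus 21.1% |
|---|---|---|
| 60 (as printed) | 0.211 to 0.449 | 0 |
| 120 | 0.246 to 0.414 | 3.5 points |
| 182 | 0.262 to 0.398 | 5.1 points |
| 364 | 0.282 to 0.378 | 7.1 points |

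**4. Which results change band.** With 60 recruited, the observed rate is 60/N. It clears 21.1% if N ≤ 284 (60/0.211 = 284.4) and clears 26.17%, the unrounded limit for 182, if N ≤ 229 (60/0.2617 = 229.3). Pilots that approach 230 to 284 men (26.1% down to 21.1%) therefore fall in the remedial band under the printed cut and in the stop band under the recomputed one. At the lower edge, 60/284 has a 95% interval of (0.164, 0.259), wholly below 33%.

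**5. Chance of clearing each cut.** Assume approaches continue until 60 men are recruited. The chance of clearing a cut c is then P(Bin(⌊60/c⌋, true rate) ≥ 60).

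| True rate | Clears 21.1% (N ≤ 284) | Clears 26.2% (N ≤ 229) |
|---|---|---|
| 22% | 66% | 7% |
| 24% | 89% | 24% |
| 26% | 98% | 50% |
| 33% | over 99.9% | 99% |

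At a true 24%, the limits for 120 and 364 approached (N ≤ 244 and N ≤ 212) are cleared 44% and 8% of the time.

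**6. Check on the stopping assumption.** With exactly 182 approached instead, the chances of clearing 21.1% and 26.2% are 60% and 9% at a true 22%, 81% and 25% at 24%, and 93% and 48% at 26%. The contrast does not depend on recruiting to exactly 60.

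**The case against.** The strongest reply is that the sum is right for the n it states, and that the working rule is a fixed cut on a clearly defined observed rate. It can be applied as printed. Between 21.1% and 33% the trial does not pass freely, because remedial work is required; below the cut the steering committee decides. SAP 9.3 and Table 2.3 already call for the observed rate with its own 95% interval on men approached, and protocol section 8.3 also ties progression to a confidence interval. The committee should therefore see the precision on the correct denominator.

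It can also be said that 182 is not in the documents. It joins 60 recruits to a 33% rate, whereas the SAP derives the 60 from accrual per centre per month. And a lower limit around the target is a weak feasibility rule in any case, since it rises with the number of men approached, whatever rate the main trial needs.

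Most of this stands as a limit on the weight of the point. The fault lies in the denominator and not in the arithmetic, the 5 points are conditional on 182, and nothing here shows that a rate of 21% to 26% is unfeasible. The mismatch itself remains. No place in either document makes 60 the number approached, every assumed number from 120 to 364 gives a limit above 21.1%, and section 11 prescribes referral to the committee only below the printed cut.

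**Conclusion.** The concern holds. The 21.1% cut is the 95% lower limit for 33% with 60 men approached, but the pilot plans to recruit 60. With about 182 approached the limit is 26.2%, so the cut is about 5 points more lenient than its stated basis (3.5 to 7 points for 120 to 364). Those sizes rest on the SAP's own formula and on an assumed number approached.

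The practical effect is confined to pilots whose true rate is well below 33%. There it is large: at a true 24%, 89% clear the printed cut against 24% for the recomputed one. At 33% the two differ by about one point. This should be corrected before the analysis, but it does not make the pilot unanalysable.

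**What to change.** Amend SAP section 11 before the feasibility analysis in one of two ways.

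- **(a) Recompute.** State the expected number approached per trial, recalculate the interval on it and align the three bands: a lower limit of about 26.2% for 182, or 24.6% to 28.2% for 120 to 364. The number must be fixed in advance because the limit rises with it. This makes the criterion harder to clear at true rates of 22% to 26% (66% falls to 7% at 22%, and 98% to 50% at 26%), so the sponsor and steering committee need to agree it. At a true 33% the cost is about one point.
- **(b) Keep 21.1% as a floor.** Justify it on its own grounds, such as the lowest rate at which the main trial could still be delivered, and remove the statement that it comes from the 95% interval. This costs a wording change and a short justification.

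Under either option the final decision below the cut stays with the steering committee. The same edit should say whether men approached are counted separately for CHRONOS-A and CHRONOS-B. SAP 6.3 has both trials offered together, while SAP 8.3, SAP 9.2 and protocol section 5.1 point to separate counts.

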2.4 Feasibility and Pilot Endpoints

CHRONOS-A and CHRONOS-B Pilot Outcome Measures

Primary

 Feasibility and acceptance of randomisation (rate per-month per-centre averaged) and compliance to allocated arm.

Secondary

IP4 - CHRONOS 19CX5006 Imperial College London Date: 13th July 2022	Short Title: IP4 - CHRONOS	Protocol No: 19CX5006	Sponsor: Imperial College London	
---	-------------------------------	--------------------------	-------------------------------------	--

- Patients' experience of consent and recruitment, including reasons for declining participation.
- Patients' motivation to accept randomisation to, and compliance with an intervention and understanding of each trial arm.
- Patients' experience of each arm including systemic issues, erectile dysfunction, urinary symptoms and rectal symptoms.
- Healthcare professionals' attitudes to intervention arms and trial design and whether this might impact on recruitment.
- Potential improvements to recruitment processes.
- To establish the feasibility of an economic evaluation alongside the main trial.

Feasibility will be measured based on a point-estimate of recruitment rates. Eligibility will be assessed against pre-defined eligibility criteria. The reasons for ineligibility will be recorded and compared across CHRONOS-A and CHRONOS-B. The retention/compliance rate will be defined as the number of participants completing study interventions and any follow-up imaging and biopsy. The reasons for withdrawal will be documented with a questionnaire given to individuals.

The integrated qualitative component is designed to inform the primary and secondary trial objectives in the trial recruitment and testing stages. Participant interview data highlighting trial processes in need of improvement may be used in real time to allow timely protocol amendments in order to improve recruitment and retention of participants. We will also interview healthcare professionals (physicians, nurses) responsible for recruiting patients.

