5. PROCEDURES AND MEASUREMENTS

5.1 Identification and recruitment of patients

All men diagnosed with prostate cancer that go before a multidisciplinary team (MDT) meeting or a tumour board, as well as any man meeting the eligibility criteria prior to MDT or tumour board discussion, will be identified for screening. Members of the clinical team or MDT / tumour board will identify patients suitable for CHRONOS. The treating clinicians will mention the study and then the local research nurses/fellows or clinical trial coordinators or clinical trial practitioners, or the treating clinicians, will then approach the patient to ascertain whether they are interested. After an initial discussion, the Patient Information Sheet (PIS) for either CHRONOS-A or CHRONOS-B, or both, if appropriate, will be given or emailed or posted to the patient. Those patients already aware of their diagnosis can be approached by telephone to enquire as to their interest in the study, so that a PIS can be sent out by email or post, prior to a clinical visit. Patients will be given a minimum of 24 hours to read the PIS before consenting to participate. Each centre will be asked to keep a screening log to determine acceptability to the study and its two randomisations.

Patients who are due to discuss the trial in clinic with their clinician will be approached for participation in the embedded qualitative research. The qualitative research information sheet will be sent to them by post or email, or by hand, and if they agree, written informed consent will be taken on the day of the consultation.

Healthcare professionals participating in the study will be approached for participation in the embedded qualitative research. The qualitative research information sheet will be sent to them by post or email or by hand and if they agree, written informed consent will be taken on the day of the consultation.

We anticipate most patients will be recruited via formal recruitment sites, however if due to local resource capabilities, recruitment may also include Patient Identification Centre (PIC) sites.

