6.3. Study Population

Men with non-metastatic prostate cancer who are suitable for focal therapy and radical therapy will be approached for recruitment into CHRONOS (CHRONOS-A and CHRONOS-B offered simultaneously).

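### The SAP's progression rule rests on the share of approached men who consent and has no accrual criterion, although the protocol's primary pilot endpoint is a rate per month per centre

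*SAP*

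**What the plan says.** **The rule.** SAP section 11 sets three bands on the recruitment rate of each trial. Below 21.1% the results suggest stopping, and the TSC makes the final decision. From 21.1% to 33% calls for remedial work. At the top, "If the recruitment rate is greater than or equal to 33%, the trial will be deemed feasible". The cuts come from a precision statement: "For a predicted sample size of 60 participants per trial", "the 95% confidence interval for an estimated recruitment rate of 33% is (0.211, 0.449").

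**The quantity tested.** SAP 5.1: "Recruitment is defined as total number of patients recruited (consented) out of the total number of patients approached". SAP 9.3 repeats this. It is a proportion with no time element.

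**The endpoint.** Protocol 2.4 gives the primary pilot outcome as "Feasibility and acceptance of randomisation (rate per-month per-centre averaged) and compliance to allocated arm", and SAP 9.2 repeats it. SAP 6.6.1 says the centres involved "would require between 1-2 patients recruited per-centre per-month"; SAP 6.6.2 and protocol 8.1.1 say the same. The pilot plan is 60 men per trial from 6 centres in 12 months.

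**Other places that touch progression.**
- SAP 9.3 reports men recruited and randomised per open centre-month and plots actual against target, with no threshold on either. It does set thresholds on treatment and drug compliance.
- Protocol 8.2 says main-stage timelines will be adjusted to the pilot's rate.
- Protocol 8.3 makes the main study depend on a minimum target recruitment rate and on funding, but gives no figure for that rate.

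**Who is approached.** SAP 6.3 describes the trials as "CHRONOS-A and CHRONOS-B offered simultaneously", and protocol 1.2 also says all patients would be offered both. Protocol 5.1 has the information sheet given "for either CHRONOS-A or CHRONOS-B, or both, if appropriate". The footnote to SAP Table 2.3 divides by all people approached. SAP 8.3 lists numbers approached for CHRONOS-A and CHRONOS-B without saying whether the counts are shared.

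**The concern.** The pilot has to show two things: that men accept randomisation, and that enough of them arrive per centre per month to fill trials of 1190 and 1260 men. The rule tests only the first. A pilot that approaches few men and persuades a third of them receives the top label, however slowly it accrues.

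The acceptance rate is itself not fully defined. A man can join only one of the two trials. If he was offered both and counts in both denominators, joining one lowers the rate of the other. The label would then depend partly on how sites hand out information sheets and not only on men's willingness to take part.

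**Working it through.** **1. The plan's own figure.** Wald interval, p = 0.33, n = 60:
0.33 ± 1.96 × √(0.33 × 0.67 / 60) = 0.33 ± 0.119 = (0.211, 0.449). This reproduces SAP section 11. The n of 60 is the number of men to be recruited, whereas the rate is defined on men approached.

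**2. Planned and required accrual, per trial.**
- Pilot exposure: 6 centres × 12 months = 72 centre-months.
- Plan: 60/72 = 0.83 men per centre-month.
- Requirement of 1-2 per centre-month over the same exposure: 72 to 144 men.
- Main-stage pace: CHRONOS-B is stated at 20 per month (SAP 6.6.2). For CHRONOS-A, 1190 men over the 5-year recruitment period in protocol 8.2 is 1190/60 = 19.8 per month.
- Centres implied at 20 per month: 20/1 = 20 down to 20/2 = 10.

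**3. A slow pilot under the rule (illustrative counts).**
- 90 approached, 30 consented: 30/90 = 33.3%, in the top band.
- Accrual: 30/72 = 0.42 per centre-month, even if every consented man is randomised.
- Centres needed for 20 per month: 20/(30/72) = 48.

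**4. Would the compliance thresholds catch it?** Suppose all 30 men, in CHRONOS-A, receive their treatment. The exact (Clopper-Pearson) 95% lower limit for 30/30 is 88.4%, above the 80% threshold. By arm, 15/15 gives 78.2%, which is the remedial band. The SAP does not name its interval method. Any effect comes from small numbers and not from speed: the same 30 men recruited over twice the centre-months would give the same limits.

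**5. Bands for an accrual criterion.** The exact 95% Poisson lower limit for a count of 60 is 45.8, so 46 men in 72 centre-months, or about 0.64. If true accrual equals the plan (Poisson mean 60), P(fewer than 60) = 0.48 and P(45 or fewer) = 0.03. A single hard floor at 0.83 would therefore fail an exactly on-plan trial about 48% of the time, which is why a middle band is needed.

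**6. The denominator (illustrative counts).** 300 men are offered both trials; 60 join A and 60 join B.
- Shared denominator: 60/300 = 20.0% in each trial, below 21.1%, so a stop recommendation for both.
- Combined uptake: 120/300 = 40%, and each trial has met its target of 60.
- Under a shared denominator, both trials can exceed 21.1% only if combined uptake exceeds 2 × 21.1% = 42.2%, and both can reach 33% only at 2 × 33% = 66% or more.
- With separate denominators none of this follows.

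**The case against.** **Accrual is not ignored.** Men per open centre-month is a primary analysis in SAP 9.3, a target graph is drawn, protocol 8.2 promises to adjust timelines, and protocol 8.3 has its own progression rule. All true. But none of these sets a number, so none stops the top label in SAP section 11 from being given to a slow pilot.

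**The rule is not the only threshold.** The compliance thresholds in SAP 9.3 also bear on progression, and compliance is part of the stated endpoint. This stands: it would be wrong to say that consent alone governs the whole decision. They do not measure speed, though.

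**The 48 centres are hypothetical.** The documents give no main-stage centre number. Protocol 8.2 plans referral between sites so that most UK sites can take part, and section 3 allows international sites. The figure shows scale and is not a forecast.

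**Stronger readings to avoid.**
- A reader might infer that the rule would stop both linked trials while the design is working. The documents do not support that. The double result needs a shared denominator, which protocol 1.2, SAP 6.3 and the Table 2.3 footnote favour but protocol 5.1 and SAP 8.3 leave open. Below 21.1% the outcome is a recommendation, the TSC decides, and Table 2.1 would show it the A:B split.
- A reader might also set these cuts beside the earlier focal-therapy pilot, in which 70 of 244 eligible men accepted randomisation. That is a different numerator and denominator and is no benchmark for consent among men approached.

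**Conclusion.** The main point holds. SAP section 11 can call a trial feasible at any accrual speed, and no other numeric criterion in either document closes the gap. In the example the pilot passes at 0.42 men per centre-month, half the planned 0.83 and below the 1-2 said to be required. This rests on reading the recruitment rate as SAP 5.1 and 9.3 define it, on the planned 6 centres all being open for 12 months, and on illustrative counts.

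The secondary point is narrower: the approached denominator for each trial is not stated. With 60 + 60 joining out of 300, each trial reads 20% if the denominator is shared. With separate denominators the rates could be higher, and the same uptake need not lead to a stop recommendation.

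The change should be made before the pilot is analysed, because this rule informs whether trials of 1190 and 1260 men open.

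**What to change.** **In SAP section 11, with a cross-reference in protocol 8.3,** add a criterion for each trial on randomised men per open centre-month, in three bands like the existing rule:
- 0.83 or more (the planned 60/72): feasible;
- from about 0.64 (46 men in 72 centre-months) to below 0.83: remedial work;
- below about 0.64: to the TSC for decision.

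If the open centre-months differ from 72, recompute the lower limit. Call a trial feasible only if it meets both the acceptance and the accrual criteria. Because 0.83 is itself below the stated 1-2, show that requirement and the implied number of main-stage centres beside the result; at 0.83, 20 men per month needs 20/0.833 = 24 centres.

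**On the denominator,** state for each trial which approached men are counted, including men given one information sheet and men given both. Present combined uptake (each man counted once) and the A:B split to the TSC beside the per-trial rates. Do not apply 33% and 21.1% to combined uptake without re-deriving them: they were set per trial with n = 60.

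**Cost.** Wording in the SAP and a cross-reference in the protocol. Screening logs, numbers approached and randomisation dates are already collected. The downside is that a slow-accruing pilot can no longer be called feasible on acceptance alone, and a trial running exactly to plan would land below the top band about 48% of the time, nearly always in the remedial band.
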